## PROTOCOL PILOT STUDY:

1. Sign COVID screening at the lobby
2. SIGN CONSENT
3. ETDRS- eyes check (screening)
4. MONOFILAMENT TEST- put the shoes on (screening)
5. Vestibular examination: (screening)- Dizziness Handicap Inventory (DHI) questionnaire (in REDCAP)
6. Auditory screening for the control group (screening older controls for ARHL rather than a full audiogram to everyone).

---

Exclusion due to one of the followings:

- ETDRS - visual impairment above 20/63
- MONOFILAMENT - No protective sensation at the bottom of their feet.
- DHI- Participants will be included with a score of 10 or below indicating no more than minimal dizziness.
- Auditory screening – participants in the control group that will exhibit a PTA higher than 40 dB (0.5–4 kHz) in the better ear (moderate HL and above) will be excluded.

---

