### **Data analysis:**

Each variable was inspected for extreme outliers (i.e., data points that fell more than 4 standard deviations [SD] away from the mean) using summary statistics and box plots. An extreme outlier was excluded from the final analysis. Normality of the variables was determined based on skewness and kurtosis. Number that is greater than +1 or lower than -1 indicate a substantially skewed distribution. For kurtosis, if the number is greater than +1, the distribution is too peaked and less than -1 indicates a distribution that is too flat. If the distribution was found to deviate from normality, non-parametric statistical analysis was conducted.

Descriptive statistics described the study sample for age, sex, height, weight, race, current medication, education level, exercise level, DHI, ABC, history of falls, MoCA and HI- MoCA. To determine if the groups are similar with respect to background measures and demographics a comparison of the three groups Normal hearing, Mild BHL and > Moderate BHL (moderate, moderately-severe, severe and profound) was done using one-way analysis of variance (ANOVA) or non-parametric Kruskal-Wallis Test for continuous measures and Chi-square analyses for categorical measures (e.g., gender).

For Aim #1: Compare single task (=ST) gait parameters between individuals age and education-matched with Mild BHL, > Moderate BHL and controls with Normal hearing and Aim #3: Compare the effect of a cognitive task on gait parameters (=DT) between age and education-matched people with Mild BHL, > Moderate BHL and control with Normal hearing: For the primary outcome measure, gait speed and its variability, and secondary outcome measures (stride length, stride time and their variability) during the 1-min walk, a mixed model repeated measures (RM)- ANOVA was conducted with 1 within-factor (task) of 2 levels (ST and DT ['subtraction 3']) and 1 between factor (group) of 3 levels (Normal hearing, Mild BHL, Moderate BHL). When the distributions were found to deviate from normality the Kruskal-Wallis' test was conducted for a between-group comparison and the Wilcoxon signed-rank test for a within-group comparison. Since I had a significant difference with age, I adjusted for age the ANOVA comparison.

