Partial Eta Square (PET) Effect Size was reported for each main effect and interaction (small effect, PET  $\geq 0.08$ ; middle effect, PET  $\geq 0.20$ ; and high effect, PET  $\geq 0.32$ ). P-values with a value of  $p < 0.05$  were considered statistically significant. Bonferroni corrections were applied to post hoc comparisons as applicable.

For Aim #2: Compare cognitive function (i.e., the Neurocognitive Index) between individuals age and education-matched with Mild BHL, > Moderate BHL and controls with Normal hearing. One way ANOVA (or non-parametric Kruskal-Wallis Test) was used to compare the Neurocognitive Index between the three groups. Moreover, one way ANOVA (or non-parametric Kruskal-Wallis Test) was used to compare the secondary outcome measures, i.e., Composite Memory, Verbal Memory, Visual Memory, EF, Cognitive Flexibility, Complex RT, Working Memory and Sustained Attention and the cognitive ST and DT performance. I used one-way ANOVA with the dependent variable, the cognitive domain (Neurocognitive Index or any of the secondary outcome measures), and group as independent variable. For the raw scores I used the ACNOVA to adjust for age since we had significant age difference and these results do not present an age-matched score. Cohen's d effect size was calculated per comparison and was defined 'small' effect size as  $d = 0.2$ , 'medium' effect size as  $d = 0.5$  and a 'large' effect size as  $d = 0.8$ .

For Aim #4: Explore whether cognitive performance (i.e., the Neurocognitive Index) is correlated with DTC per group. One way ANOVA (or non-parametric Kruskal-Wallis Test) was used to compare the DTC between the three groups. Correlations between the cognitive domains and DTC were assessed using Pearson's correlation (or its non-parametric equivalent Spearman's, if the distributions are found to deviate from normality) for continuous variables. Pearson's correlation for each comparison was defined as 'little to none' for  $r = 0-0.24$ , 'fair' for  $r = 0.25-0.49$ , 'moderate to good' for  $r = 0.50-0.74$  and 'good to excellent' for  $r = 0.75-1.00$ . SPSS version 27 IBM (NY, US) was used for all statistical analysis.

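### The control hearing screen admits mild loss, but controls are analysed as Normal hearing against a separate Mild BHL group, and no rule places mild-range controls

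*Combined protocol and SAP*

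**What the plan says.** **Entry.** In the exclusion list after step 6 of the pilot study protocol, the only hearing rule for controls excludes "participants in the control group that will exhibit a PTA higher than 40 dB" in the better ear over 0.5–4 kHz. The rule itself describes what it removes as moderate loss and above. Step 6 describes a screen of older controls for age-related loss in place of full audiometry for all.

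**Analysis.** The Data analysis section names three groups: "Normal hearing, Mild BHL and > Moderate BHL (moderate, moderately-severe, severe and profound" forms of loss make up the third. Aims 1 and 3 compare people with "Mild BHL, > Moderate BHL and controls with Normal hearing", using a repeated-measures ANOVA with "1 between factor (group) of 3 levels (Normal hearing, Mild BHL, Moderate BHL" as levels. Aim 2 compares cognition across the same three groups. Under Aim 4, a one-way test "was used to compare the DTC between the three groups".

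**Not stated.** The text gives no PTA value separating Normal hearing from Mild BHL, and no instruction for a control whose PTA falls in the mild range.

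**The concern.** The entry rule and the analysis labels use different boundaries. At entry, the line for a control is drawn between mild and moderate loss. In the analysis, the line for the reference group is drawn between normal hearing and mild loss. A control with mild loss meets the entry rule but does not fit the label given to the reference group.

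Hearing group is the between-subject factor for the primary gait outcomes, for cognition and for the dual-task cost comparison. If mild-loss controls are counted as Normal, the Normal-versus-Mild difference is pulled toward zero, and a null result could not be told apart from a mixed reference group. The age adjustment ("Since I had a significant difference with age, I adjusted for age the ANOVA comparison") deals with a different imbalance and does not correct a wrong hearing group. Even if no one was misplaced, a reader cannot reproduce the grouping from the document.

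**Working it through.** The plan gives no group sizes, means, PTA data or power calculation, so there is no figure of its own to reproduce. The check has two parts.

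**1. The passages side by side**

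| Better-ear PTA of a control | Exclusion list | Data analysis |
|---|---|---|
| Above 40 dB | Excluded; not moved to a hearing-loss group | Not applicable |
| Mild range: from an unstated lower bound up to 40 dB | Stays in the control group | Not stated: controls are labelled Normal hearing, yet Mild BHL is a separate level |
| Below the unstated lower bound | Stays in the control group | Normal hearing |

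- That mild loss passes the screen needs no outside hearing scale. The document equates a PTA above 40 dB with moderate loss and above, so mild loss lies at or below 40 dB.
- The same wording implies 40 dB as the upper edge of mild. Only the lower edge and the placement of the middle row are missing.
- A control with moderate loss is excluded rather than reassigned. The plan contains no mechanism that moves a control into a hearing-loss group, so nothing written takes the middle row out of the reference level.

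**2. Size of the dilution, if it occurs**

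Assumed inputs, none of them in the documents:

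- p = share of the Normal group with mild loss
- k = how far those people lie from the true Normal mean toward the Mild mean (1 = at the Mild mean)
- D = true Mild mean minus true Normal mean

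Observed Normal mean = (1 − p) × Normal mean + p × (Normal mean + kD) = Normal mean + pkD.

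Observed difference = D − pkD = D(1 − pk), so the fraction lost is pk.

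| p | k = 0.5 | k = 1 |
|---|---|---|
| 0 | 0% | 0% |
| 0.10 | 0.10 × 0.5 = 5% | 0.10 × 1 = 10% |
| 0.25 | 0.25 × 0.5 = 12.5% | 0.25 × 1 = 25% |

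If effects run in the same direction across the three levels, the difference between Normal and the moderate-or-worse group loses the same absolute amount, pkD, which is a smaller proportion of a larger difference. The expected mean difference between Mild and moderate-or-worse does not involve the reference group and does not change.

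This covers mean differences without the age covariate. It does not cover the Kruskal-Wallis route or the Aim 4 correlations.

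**The case against.** The strongest reply is that the exclusion list governs entry to the study, not placement in an analysis group. The groups are defined by hearing level, so a control found to have mild loss would naturally be analysed as Mild BHL, and all that is missing is one sentence of definition.

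Part of this stands. A reader might infer that the analysed Normal group did contain people with mild loss. The documents do not support that: no PTA data are given, and the groups may have been formed from measured PTA. But the reply has no text behind it either. The reference group is repeatedly called controls, no reassignment step is written, and controls above 40 dB are dropped rather than moved.

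Three other inferences go too far:

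- **That the plan gives no PTA limit for mild loss at all.** The screen implies its upper edge, 40 dB.
- **That the effect can be put precisely on the plan's partial eta squared scale.** This would need group sizes, spacing of means and the age covariate, none of which is given. The pk range is as far as the material goes.
- **That the contrast between Mild and moderate-or-worse is biased as well.** Its expected mean difference is untouched. Moving controls into Mild BHL would change it, but that follows from classifying them correctly and is not harm done by the screen.

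**Conclusion.** The mismatch is in the text and should be fixed. As written, the reference level may include people who belong by hearing level to the Mild BHL level, and no rule prevents it. The consequence is conditional: a loss of pk in the expected Normal–Mild difference, 5% to 25% over the assumed ranges and zero if no mild-range control was analysed as Normal. The conclusion about the definitions does not depend on p or k. The percentages depend on them entirely. Confidence is medium, because a PTA-based grouping may have been applied without being written down.

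**What to change.** 1. Assign all three analysis groups by measured better-ear PTA and state the limits. Set the upper limit for control/Normal equal to the study's own lower bound for Mild BHL. That bound is not in the documents and must be supplied.
2. Analyse controls between that bound and 40 dB as Mild BHL. As a sensitivity analysis, omit them instead, so that they are in neither group. The Data analysis section is written as completed work, so naming the main analysis and reporting both results limits discretion after the fact.
3. Say how a control without a recorded PTA is handled.
4. If any mild-range control was analysed as Normal, rerun every three-group comparison, report the results before and after, and report age by group again. Step 6 is aimed at older controls, so those who move may be the older ones and the age difference may change.
5. If groups were already assigned by PTA, state that and the limits used. No rerun is then needed.

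**Cost.** One assignment rule and, only if needed, one rerun. The Normal group may become somewhat smaller, and the Mild group will change if controls join it. The fix also relies on numeric PTA having been recorded at screening, which step 6 does not confirm.

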7. TAKE OFF HEARING AID
8. Wearing the APDM on both feet and pelvic where the ISPS
9. Balance testing: Standing feet attached with E/O, Standing feet attached with E/C, foam with E/O, foam with E/C for 30 sec. (descriptive)
10. 20 min: computerized cognitive battery
11. Randomized Trial of TUG (without hearing aid):
  1. TUG - 2 repetitions
  2. TUG DT\_sub3- 2 repetitions
12. HI- MOCA or MOCA

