13. TMT A & B
14. Practice trial: Walking back and forth the corridor

15. Randomized Trial- each trial will be done 1 time (without hearing aid):

1. Single cognitive task sub1 - [Baseline] while sitting (serial subtraction of 1) + record with phone
2. Single cognitive task sub3 - [Baseline] while sitting (serial subtraction of 3) + record with phone
3. Single motor – [Baseline] Walking on the ground for 1 min a 10 m long corridor – recording with a stopwatch
4. Dual task cognitive sub1 (DT\_sub1) - serial subtraction of 1 + #3 - recorded with stopwatch + record with phone
5. Dual task cognitive sub3 (DT\_sub3) - serial subtraction of 3 + #3 - recorded with stopwatch + record with phone

Using REDCAP:

16. DEMOGRAPHIC questionnaire (descriptive)
17. ABC – In healthy young adults ask: “have you never had any concern regarding: balance?” – if yes- fill up the questionnaire. (descriptive)

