### **Instructions:**

#### **TUG:**

Instructions: “On the word GO you will stand up, walk to the line on the floor, turn around and walk back to the chair and sit down. Walk at your regular pace.”

The time to complete the test will be recorded using a stopwatch.

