### **Gait Serial Subtraction 1**

“Walk straight ahead at your comfortable speed while counting backwards out loud in jumps of 1 from a number that I will tell. Start from the next number. For example, if I say 557, you start: 556, 555 and so on. When you see the mark on the floor you turn and walk straight ahead to the opposite direction. Keep walking and counting until I will tell you to stop. The total time for walking is 1 min. If you lose your balance do whatever feels safe to stay steady. One of the researchers is going to walk next to you to prevent any fall”.

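### Dual-task instructions and start numbers are spoken after hearing aids come off, so misunderstanding of the task may differ by degree between the hearing groups

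*Combined protocol and SAP*

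**What the plan says.** All references are to the combined protocol and SAP.

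- **Aid removal.** Item 7 is "TAKE OFF HEARING AID". It precedes the balance, cognitive, TUG and walking tests, and no later step puts the aids back on. Item 11 is headed "Randomized Trial of TUG (without hearing aid") and item 15 "Randomized Trial- each trial will be done 1 time (without hearing aid").
- **Spoken delivery.** Under Instructions, the script Gait Serial Subtraction 1 asks for "counting backwards out loud in jumps of 1 from a number that I will tell". The same words stand in Gait Serial Subtraction 3. All three walking scripts tell the participant to continue until the tester says to stop. The TUG scripts begin "On the word GO you will stand up".
- **Safeguards.** Item 14 is a practice walk along the corridor. Item 12 lists a hearing-specific version of the MoCA. Nothing comparable is described for the walking or subtraction tasks.
- **Groups and analysis.** Data analysis compares normal hearing, mild loss, and a third group that runs from moderate to profound loss. The primary gait analysis crosses group with task (single task versus subtraction 3) and adjusts for age. Aim 2 compares cognitive single- and dual-task performance between groups. Aim 4 compares DTC, which I read as dual-task cost.

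**The concern.** The factor under study is hearing, and the dual task is explained and started by voice with hearing uncorrected. If participants with worse hearing more often miss or misread what they are asked to do, a group-by-task difference has two possible sources. One is the cognitive-motor interference the study wants to measure; the other is that some participants did a different task, or hesitated over it. The planned analysis cannot tell these apart. Adding an audibility covariate would not rescue it, because audibility largely is the group factor. The matter has to be settled by how the task is delivered or by checking what participants actually did.

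**Working it through.** The documents give no sample size, standard deviation or effect size on this point, so there is no planned figure to reproduce. The check is mainly textual.

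**1. Which spoken elements must fall inside the unaided period?** The documents do not say when each script is read; reading after removal follows from the order of the steps. The start number and the stop cue belong to the trial itself, so they are necessarily given unaided. No script is printed for the seated subtraction tasks, so spoken delivery there is an inference.

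**2. Which elements reach an analysed outcome?** Let s be the effect of speech demands common to both walks in a group, and d the effect of those found only in the dual task (start number, counting instruction).

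- Single-task walk: carries s.
- Dual-task walk: carries s + d.
- Dual minus single: (s + d) − s = d.
- Group-by-task contrast for groups A and B: d(A) − d(B).
- Average over the two tasks: [s + (s + d)]/2 = s + d/2.

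The shared part cancels in the interaction, but the dual-task part does not. Counting performance in the dual task is compared directly between groups, so nothing cancels there. Each item 15 condition is run once, so a misunderstood trial is not averaged out.

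**3. The step size.** The two dual-task walking scripts side by side, both using 557 as the example:

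| Script | Sequence implied by the wording | Sequence in the example |
|---|---|---|
| Subtraction 1 | 557 − 1 = 556, then 555 | 556, 555 |
| Subtraction 3 | 557 − 1 = 556, then 555 | 557 − 3 = 554, then 551 |

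The subtraction-3 script, which feeds the primary contrast, states one step and illustrates another. A listener must settle the conflict by ear, and those with the worst unaided hearing are least well placed to do so.

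**4. Direction.** A participant who counts down in ones during the subtraction-3 walk does an easier task, which would shrink that group's apparent dual-task cost. One who is unsure and hesitates may slow down or miscount, which would enlarge it. The sign is therefore open.

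**5. Size, by illustration only.** Assume no true group difference, equal groups of n, and an artefact that shifts the three group means by 0, b/2 and b standard deviations. For a one-way ANOVA at 0.05, the form planned for DTC, the noncentrality is n × [(b/2)² + 0 + (b/2)²] = n·b²/2 on 2 and 3n − 3 degrees of freedom. Both n and b are assumptions.

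| n per group | b = 0 | b = 0.2 (noncentrality) | b = 0.5 (noncentrality) |
|---|---|---|---|
| 10 | 5.0% | 6.4% (0.20) | 14.3% (1.25) |
| 20 | 5.0% | 8.0% (0.40) | 26.1% (2.50) |
| 30 | 5.0% | 9.6% (0.60) | 38.1% (3.75) |

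Entries are the chance of a significant group effect. Nothing in the documents says where b lies.

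**The case against.** The best case for the plan is that unaided testing may be a deliberate way to standardise the exposure, and that a short bench checklist need not record every courtesy a tester extends. Serial subtraction is also not a listening task: the number is given once and the participant then generates the sequence aloud. Participants count out loud and the item 15 counting trials are phone-recorded, so errors can be found. A researcher walks beside the participant, which may help audibility. Much of this stands. Removing the aids is not the error, and the gap lies in how the dual task is delivered. But the documents describe no confirmation step, and detectable errors help only if someone looks for them.

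Several stronger readings are tempting and are not supported:

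- **That the gait comparison is contaminated.** The documents show a route for bias but no amount.
- **That only the hearing-loss groups can mishear.** The control screen excludes a better-ear PTA above 40 dB, so controls with reduced hearing can enter. The contrast is one of degree.
- **That late reactions to a spoken start distort the results.** The start word appears only in the TUG scripts, and Data analysis names no TUG outcome.
- **That a misheard start number lightens the load by some fraction.** Subtracting from a wrong number is the same kind of task; a wrong step size is what would change it.
- **That unheard stop cues are a safety failing.** A researcher is alongside to prevent falls, and a missed cue would mainly lengthen the walk.

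**Conclusion.** The concern holds as a group-linked alternative explanation for the dual-task results, namely the group-by-task contrast in gait (Aim 3), cognitive single- and dual-task performance (Aim 2) and DTC (Aim 4). The weakest link is the seated single task, for which no script is given. Size and direction are unknown: under the assumptions tabulated above, the false-positive chance ranges from close to the nominal 5% to several times that. The conclusion rests on two premises: that the scripts are delivered as written, and that no unrecorded visual aid or comprehension check was used. If the recordings show that participants in all groups started from the right number and used the right step, a misperformed task is largely ruled out as an explanation for the collected data.

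**What to change.** **For further testing.** Keep the aids off, and do the following identically in all three groups:

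- Give the instruction immediately before each trial as a printed script, with the participant repeating the task back.
- Show the start number on a card.
- Use a visual or tactile start and stop signal.
- Correct the subtraction-3 script so that its wording agrees with its example.

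Moving the instructions to before item 7 is not a good substitute. Participants would have to carry them through balance testing and a 20-minute cognitive battery, which adds a memory load to a study that compares cognition. Vision is already screened at entry, so printed material is feasible.

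**For data already collected** (Data analysis is written in the past tense). Review the item 15 phone recordings without knowledge of group. Code each counting trial for step size and, where the assigned number is audible or was noted, for the start number. Report the counts by group, repeat the Aim 2, 3 and 4 analyses without the affected trials, and state the limitation. Because each condition was run once, excluding a trial removes that participant from the paired contrast, so the result is a sensitivity analysis and not a replacement.

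**Cost.** Cards, a hand signal, revised script wording and some hours of listening to recordings. No extra visit is needed.
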